1.4.3 Study “stopping” rules

The following stopping rules based on potential toxicities will serve as the basis for placing the study on hold. Although the stopping criteria do not incorporate an absolute requirement for causality, the potential relationship between an AE and CFZ533 will be evaluated carefully on a case-by-case basis between the Sponsor and the Investigator. Following a review of the AE(s), a decision to permanently discontinue enrollment or re-initiate CFZ533 dosing will be made by the DMC.

- Two (2) or more patients presenting with post-transplant lymphoproliferative disease or progressive multifocal leukoencephalopathy in the CFZ533 treatment arm.

In addition, specific stopping rules for the incidence of tBPAR will be applied. These rules are designed to ensure that an arm will be stopped if there is high probability ($> 90\%$) that the true tBPAR rate is greater than 20%. Based on this stopping rule, the maximum number of patients with tBPAR for various different illustrative sample sizes would be as follows:

Table 1-1 Study stopping rules for tBPAR

Total number of patients (N)	Number of patients with tBPAR that would lead to stopping the treatment arm (n)	Observed tBPAR rate (n/N)
3	2	0.67
4	2	0.50
5	3	0.60
6	3	0.50
7	3	0.43
8	4	0.50
9	4	0.44
10	4	0.40
11	5	0.45
12	5	0.42
13	5	0.38
14	5	0.36
15	6	0.40
16	6	0.38
17	6	0.35
18	6	0.33
19	7	0.37
20	7	0.35
21	7	0.33
22	7	0.32
23	8	0.35
24	8	0.33
25	8	0.32
26	8	0.319
27	9	0.33
28	9	0.32
29	9	0.31
30	9	0.30

In addition to the automatic hold criteria and tBPAR criteria presented above, the DMC will review safety data regularly as outlined in their charter during quarterly and ad hoc meetings. The DMC can recommend stopping a specific study arm(s) or the entire trial if significant changes or effects that, in their collective opinion, are deemed unsafe or unethical to continue administering CFZ533.

2 First interpretable results (FIR)

First interpretable results (FIR) will be provided for this trial.
Corporate Confidential Information

Corporate Confidential Information

4 Statistical methods: Analysis sets

For patients for which the actual treatment received does not match the randomized treatment, the treatment actually received will be used for the analysis.

The Full Analysis Set will include all patients that received at least one dose of study drug and who were transplanted.

The modified Full Analysis Set (mFAS) will include all patients that received at least one dose of study drug and who were transplanted that also meet the following conditions:

- Donor age < 65 years
- Cold ischemic time (CIT) < 18 hours
- HLA mismatches at DR locus
- HLA total mismatches < 5

The Safety Analysis Set will include all patients that received at least one dose of study drug. All patients that receive their transplant along with any patient who receive study drug but have no transplant will be combined.

The PK analysis set will include all patients with at least one available valid (i.e. not flagged for exclusion) PK concentration measurement, who received any study drug and experienced no protocol deviations with relevant impact on PK data.

The PD analysis set will include all patients in the Full Analysis Set with any available PD data and no protocol deviations with relevant impact on PD data.

The protocol deviation codes are described in detail in the data management plan.

5 Statistical methods for Pharmacokinetic (PK) parameters

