3.1.2 All cohorts

Before any study-related evaluations are performed, the patient must give written informed consent. Once consent is obtained, pre-transplant screening and baseline assessments will occur to determine the patient's eligibility to participate in the study starting up to 28 days prior to transplantation. If the screening, baseline and study Day 1 visits occur in close proximity of each other (i.e., within a 12 hour timespan), certain repeated assessments may be omitted, as noted in the [Assessment schedule](#). Data collection from assessments performed at the clinical site as part of medical standard of care but prior ICF sign-off is acceptable in order to confirm patient eligibility for patients receiving an organ from a deceased donor, if assessed shortly before transplantation (i.e within 24h – matching the baseline window of Day -1 to Day 1) and in-line with inclusion and exclusion criteria.

Day 1 is defined as the day of randomization/enrollment and transplantation. This protocol defines 7 days to a week and 4 weeks (or 28 days) to a Study Month. For example, Week 2 is considered to start on Day 8 and Study Month 2 is considered to start on Week 5/Day 29. Randomization/enrollment should occur within 24 hours pre-transplant and drug administration will begin after randomization/enrollment. If CFZ533 is to be administered, the first dose of CFZ533 will be administered IV pre-transplant or intra-operatively, and must be completed by the time of unclamping. Other study drugs must be started within 24 hours post-transplant or according to local practice.

Patients who are randomized/enrolled but not transplanted will be replaced. All randomized/enrolled subjects are expected to continue in the study up to Month 6 (Part 1) or Month 12 (Part 2) regardless of being on or off randomized/assigned treatment. All subjects will be followed-up for safety (e.g., SAEs) for approximately three months after their last dose of CFZ533 or 2 months after the EoS visit for patients on SoC treatment.

[figure not shown]
Any treatment arm in which the rejection rate fulfills the *a priori* defined stopping rules (see [Section 5.5.10](#)) will be immediately discontinued at any time during the study.

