5.4 Treatment blinding

This is an open-label, exploratory study and it is not planned to blind patients or site staff to treatment. In Part 1 since there is just one treatment arm, it will be known to the whole Clinical Trial Team that the subjects all received 3mg/kg CFZ533. In Part 2, core Clinical Trial Team members will be unblinded to continuously review safety and clinical data and evaluate the stopping rules.

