9.4 Analysis of the primary variable(s)

9.4.1 Variable(s)

Parts 1 and 2:

The primary variable is tBPAR after 3 months of treatment. For the analysis in Part 2, the total “on treatment time” in each treatment group is required.

Corporate Confidential
Information

Corporate Confidential Information

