9.6 Sample size calculation

All Parts:

The stopping rules as defined in [Section 5.5.10](#) are designed to ensure that a CFZ533 treatment arm will be stopped if there is a high probability (>90%) that the true tBPAR rate is greater than 20%.

[Figure 9-1](#) indicates the probability of stopping for an arm for various true tBPAR rates and shows that the stopping rules ensure that the chance of stopping an arm are sufficiently high for true high tBPAR rates while remaining appropriately low when the true rates are low.

Figure 9-1 Probability of stopping a cohort for various true tBPAR rates

Part 2

Operating characteristics

The sample size justification for Part 2 considers the probability of progressing further development or not progressing based on the planned safety stopping rules and the success criteria for the planned sample size.

The safety stopping rules (see [Section 5.5.10](#)) ensure that the study will not continue if:

$\Pr(\theta_{CFZ533} > 0.20 \mid \text{data}) > 90\%$

[figure not shown]
The success criteria (see [Section 9.4.2](#)) are met if:

$$\Pr(\theta_{CFZ533} - \theta_{SoC} < 0.20 \mid \text{data}) > 60\%.$$

[Figure 9-2](#) shows the chances of continuing development (i.e., of not meeting the safety stopping rules and meeting the success criteria) on the y-axis for a range of true values of the tBPAR rate for CFZ533 (x-axis) and for three possible control rates (blue and grey curves). The probability of moving is high when CFZ533 has a low true tBPAR rate and is comparable to control. For example, if the true CFZ533 rate is less than 20% and the true control rate is around 10%, there is a greater than 80% probability of progressing to Part 3.

Conversely, when the true tBPAR rate for CFZ533 is high, the probability of not continuing is high. For example, there is an approximately 80% probability of not progressing when the true CFZ533 rate is more than 25% greater than the true control rate.

Figure 9-2 Probability of progressing for different true values of tBPAR for CFZ533 and control

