6.1.3 Statistical model, assumptions and hypotheses

The number of patients with tBPAR is assumed to follow a binomial distribution, i.e.,

$$r_i \sim \text{Binomial}(n_i, \theta_i)$$

where r_i is the number of patients with tBPAR in treatment group i , n_i is the number of patients in treatment group i and θ_i is the probability of tBPAR.

The efficacy analysis for the first 3 months of Part 2 considers whether a CFZ533 treatment arm meets the pre-defined criteria for initiation of Part 3.

The pre-defined success criteria is considered to be a tBPAR rate difference between the CFZ533 arm and the control group of less than 20 percentage points with at least 60% level of proof.

$$\Pr(\theta_{\text{CFZ533}} - \theta_{\text{SoC}} < 0.20 \mid \text{data}) > 60\%$$

The required posterior probabilities will be estimated from simulations of the posterior distributions of $\theta_{\text{CFZ533}} - \theta_{\text{SoC}}$ and compared to the thresholds for the levels of proof.

The prior distributions will be assumed to be a non-informative Beta(1/3, 1/3) for CFZ533 and an informative prior of Beta(1, 13) for SoC. This informative prior corresponds to an approximate mean response rate of 7% with a 95% confidence interval of (0.2%, 24%) and was determined via a meta-analysis of control therapies.

The posterior mean tBPAR rates for each treatment group and for the difference in mean response rates between treatments will be tabulated together with the 95% credible intervals, the number of patients with tBPAR and the posterior probabilities of being above the thresholds, 10%, 15%, 20%, 25%.

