6.1.4 Supportive analyses

Kaplan-Meier estimates

In this analysis, patients who have not experienced tBPAR, will be censored with the censoring time as defined by the last contact day at or before the cut-off point (e.g., 1st IA Month 3 visit, 2nd IA Month 6 visit). The patients will be considered as completed at the date of their corresponding analysis cut-off point. In addition to the Kaplan-Meier plot, a log-rank test shall be performed to obtain estimates with CI's for each treatment arm and the difference between treatment arms.

During data review, it was noticed that some patients were switched from the randomized treatment to another regimen. Therefore in future IA's, more focus shall be placed on the Kaplan-Meier analysis.

Supportive Bayesian analysis

In addition the Bayesian analysis will be repeated with a model using a Poisson distribution to account for the patients that may switch treatment or discontinue early from the study. The following parametrization will be used:

The number of tBPAR events in group i is assumed to follow a Poisson distribution, i.e.

$$y_i = \text{Poisson}(\mu_i),$$

where μ_i is the expected number of events in group i, with

$$\mu_i = \lambda_{i,T} * t_{i,T},$$

with $t_{i,T}$ being the total follow up time in group i (times censored at treatment switch or discontinuation) up to analysis time point T and λ_i being the event rate in group i up to the analysis time point T. For sensitivity analysis of the primary analysis the analysis time point T is week 12 (i.e. week 13 visit, month 3 after transplantation). The probability of an tBPAR event occurring up to the analysis time point can then derived as $\theta_i = 1 - \exp(-\lambda_i * T)$.

The pre-defined success criteria is considered to be a difference in the probability of tBPAR between the CFZ533 arm and the control group of less than 20 percentage points with at least 60% level of proof.

$$\Pr(\theta_{CFZ533} - \theta_{SoC} < 0.20 | \text{data}) > 60\%$$

The required posterior probabilities will be estimated from simulations of the posterior distributions of $\theta_{CFZ533} - \theta_{SoC}$ and compared to the thresholds for the levels of proof.

The prior distributions will be assumed to be a non-informative Beta(1/3,1/3) for θ_{CFZ533} and an informative prior of Beta(1, 13) for θ_{SoC} .

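### Table 1-1 meets its 90% stopping criterion only for fully followed patients, but the tBPAR rule is evaluated continuously during enrolment and neither N nor the required follow-up is defined

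*SAP*

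**What the plan says.** Protocol 9.6 states that a CFZ533 "treatment arm will be stopped if there is a high probability (>90%) that the true tBPAR rate is greater than 20"%. SAP 1.4.3 repeats the criterion: "These rules are designed to ensure that an arm will be stopped if there is high probability". SAP Table 1-1 then lists, for N from 3 to 30, the number of patients with tBPAR that stops the arm. It describes the sample sizes as illustrative.

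On timing, Protocol 3.1.2 says that an arm fulfilling the rules "will be immediately discontinued at any time during the study". Protocol 5.4 adds that in Part 2 "core Clinical Trial Team members will be unblinded to continuously review safety and clinical data and evaluate the stopping rules".

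Neither SAP 1.4.3 nor the visible protocol text says whether N means enrolled, transplanted or followed to Month 3, and neither gives the stopping rule a time horizon. The nearest horizon is that of the endpoint in Protocol 9.4.1: "The primary variable is tBPAR after 3 months of treatment". Follow-up time is used in SAP 6.1.4, where the Poisson model has an exposure term "being the total follow up time in group i (times censored at treatment switch or discontinuation"), but only as a supportive analysis of the endpoint.

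Protocol Appendix 3 contains a second tBPAR rule: 7, 8 or 9 events, depending on the control-arm count, whatever N is.

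**The concern.** A binomial posterior treats each event-free patient as a complete non-event. During enrolment many event-free patients have been at risk for only days or weeks. What the table then does depends on an undefined N:

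- **N = all enrolled.** A patient transplanted yesterday counts as a full three-month success. The posterior is understated, and the arm can continue after the stated criterion has been met.
- **N = events plus patients who completed three months.** Events enter at once and non-events wait 12 weeks. The posterior is overstated, and a good drug can be stopped.

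This rule is the main statistical protection for patients on a CNI-free regimen, and Protocol 9.6 uses it for the probability of progressing.

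**Working it through.** **Inputs.** Criterion Pr(θ > 0.20 | data) > 0.90 (SAP 1.4.3, Protocol 9.6). Prior "non-informative Beta(1/3, 1/3) for CFZ533" (SAP 6.1.3; the stopping text itself names no prior). Arm size 30 (SAP 1.4.2). Horizon 3 × 28 = 84 days (Protocol 3.1.2 and 9.4.1). Assumed, because the documents give neither: accrual of the 30 patients over 3, 6, 12 or 24 months, and rejection times either flat over 84 days or early (truncated exponential, 21-day scale).

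**Step 1: reproduce the table.** For each N, take the smallest n for which Beta(1/3 + n, 1/3 + N − n) has more than 0.90 of its mass above 0.20. All 28 rows match. The posterior at the boundary is 0.904 to 0.977; one event fewer gives at most 0.898. For example, 9/30 gives 0.904 and 8/30 gives 0.81. A Beta(1,1) prior would miss 8 rows and Beta(1/2,1/2) one.

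**Step 2: a worked state during enrolment.** Take 20 transplanted and 6 with tBPAR. Of the 14 event-free, 7 are fully followed and 7 are at 42 days. Weight each event-free patient by the fraction F of the three-month risk already passed.

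- Table, N = 20: Beta(6.33, 14.33), Pr = 0.857. Continue; the row needs 7.
- Flat hazard, F = 0.5: non-events 7 + 7 × 0.5 = 10.5; Beta(6.33, 10.83), Pr = 0.939.
- Early hazard, F = (1 − e⁻²)/(1 − e⁻⁴) = 0.88: non-events 7 + 7 × 0.88 = 13.2; Beta(6.33, 13.50), Pr = 0.880.

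The exact likelihood θ⁶(1 − θ)⁷(1 − Fθ)⁷ gives 0.951 and 0.888. In this state the criterion is met under a flat hazard and not under an early one. With 20 patients entered evenly at 4 per 28 days and the 6 events among the earliest patients, the exact posterior is 0.99 (flat) or 0.95 (early), while the table still reads 0.86.

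**Step 3: simulation.** 2,000 trials per setting, uniform entry, rule checked at every event, weighted rule started at a weighted N of 3. Mean number enrolled at stopping, true rate 40%:

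| Accrual | Flat: N = enrolled | Flat: weighted | Early: N = enrolled | Early: weighted |
|---|---|---|---|---|
| 3 months | 28.4 | 20.8 | 20.8 | 15.0 |
| 6 months | 22.2 | 16.0 | 15.3 | 12.5 |
| 12 months | 16.1 | 12.8 | 12.2 | 11.2 |

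A separate run at 24 months with early events gave 9.3 against 9.3. Eventual stopping is about 90 to 95% with N = enrolled and 93 to 96% weighted.

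Stopping at a true 10% rate with N = events plus completers is 35 / 22 / 13% (flat) and 51 / 29 / 17% (early) for 3 / 6 / 12 months, against about 5% weighted. Across all checks the ranges were about 12 to 51% and 3 to 7%. A version using the exact likelihood and Poisson accrual gave about 8 to 9% in place of the latter.

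**The case against.** **The table is correct and its rows are only illustrative.** This stands. With complete follow-up it has exactly the property claimed. A reader might infer that the table is miscalculated, and the reproduction rules that out.

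**Late stopping is an inference.** This stands too. The documents nowhere say that partly followed patients enter N as non-events. A reader might also infer that the SAP sentence fails on either meaning of N. It does not. The sentence runs one way: stop if the probability is high. N counted as events plus completers never exceeds the weighted N, so from N = 3 the arm is stopped whenever the weighted criterion is met. Over-stopping is a different fault.

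**The large delays need fast accrual and a flat hazard.** Correct. The worked state in Step 2 also exceeds 0.90 only under the flat profile.

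**Other safeguards exist.** The figures in the working leave out Appendix 3. A rough check that added it (control rate assumed 7%, flat hazard, true rate 40%) lowered the chance of enrolling all 30 without a prior stop from 81 / 37 / 15% to 66 / 24 / 10% for 3 / 6 / 12 months. Even with termination always at 7 events, mean enrolment at stopping fell only from 28.4 / 22.2 / 16.1 to 27.8 / 21.6 / 15.6. It is a partial offset. DMC review, quarterly and ad hoc, helps but is discretionary.

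**A definition may exist elsewhere.** Text after the rule in Protocol 5.5.10 is redacted, Figures 9-1 and 9-2 are not shown, and the DMC charter is not among the documents. That limits the point to the visible text, but SAP 1.4.3 prints the whole table without a definition.

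**Conclusion.** The point holds in limited form. Table 1-1 delivers the 90% criterion only when all N patients have had a tBPAR or completed three months. The rule is evaluated before that, and the SAP leaves N and the required follow-up undefined.

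With N = enrolled, the consequence is later stopping and more exposure. The excess is about 7 to 8 patients out of 30 in the least favourable case examined, and 0 to 1 with early rejections and accrual of 12 months or more. The probability of eventually stopping is little changed. With N = events plus completers, the consequence is over-stopping of a drug with a true 10% rate.

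The direction follows from the binomial model; the sizes rest on assumed accrual and rejection timing. The documents do not support saying that the rule will stop an ineffective arm late, because that is one of two possible meanings of N. They also do not show whether Figures 9-1 and 9-2 allow for staggered entry.

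**What to change.** Leave the 20%/90% criterion unchanged.

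1. In SAP 1.4.3 and Protocol 5.5.10, state what N counts and over what horizon, and that the Table 1-1 counts have the stated property only for fully followed patients.
2. For ongoing reviews, give the DMC the same posterior computed with partial follow-up, next to the raw count. The exposure-time approach in SAP 6.1.4 already assembles what is needed. Pre-specify one risk-time profile and one sensitivity profile, with their source, because the documents give none.
3. Report the operating characteristics of the rule under staggered entry and repeated looks, for a stated range of accrual.
4. Reconcile Table 1-1 with Appendix 3. At 30 fully followed patients, the Appendix 3 counts of 7 and 8 correspond to posteriors of 0.67 and 0.81, below the 90% criterion. Which rule governs is for the sponsor and DMC to settle.

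**Cost.** SAP and protocol wording and a short program at each review; no new data, visits or patients. The downside is that the profile must be fixed in advance. If a flat profile is used while rejections come early, stopping at a true 10% rate rises to about 8 to 16%, against 4 to 5% with the matching profile. That is why the sensitivity profile should be shown alongside.

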5.1 Variables

If data permit, typical exposure metrics and parameters could be determined using the actual recorded sampling times and non-compartmental method(s) with WinNonlin Pro or Phoenix, including (but not limited to): Cmax, Cmin, Cmin,ss, Tmax, from the plasma concentration-time data.

5.2 Descriptive analyses

CFZ533 plasma concentration data will be listed by treatment, transplant status (if required), patient, and visit/sampling time point. Tac and MPA trough levels will be measured and listed by treatment, visit and patient. If data permit, PK parameters will be calculated and listed by treatment and patient. Concentrations below the limit of quantification will not be considered for the calculation of PK parameters. Descriptive summary statistics will include mean (arithmetic and geometric), SD, and CV (arithmetic and geometric), median, minimum and maximum. An exception to this is Tmax where median, minimum and maximum will be presented.

Corporate Confidential Information

5.2.1 Graphical presentation of results

The CFZ533 plasma concentration data (PK) will be presented graphically in a plot of the mean concentration (unit: $\mu\text{g/mL}$; log scale) over time (unit: day; elapsed time since first dose), overlaying individual profiles over time with an overlaid mean and individual time-concentration profiles by patient.

6 Statistical methods for Pharmacodynamic (PD) parameters

6.1 Primary objective

6.1.1 Variables

The primary variable is tBPAR after 3 months of treatment.

6.1.2 Descriptive analyses

The tBPAR data will be listed by treatment. The data will be summarized and will include the number (percentage) of patients that have a tBPAR.

6.1.3 Statistical model, assumptions and hypotheses

The number of patients with tBPAR is assumed to follow a binomial distribution, i.e.,

$$r_i \sim \text{Binomial}(n_i, \theta_i)$$

where r_i is the number of patients with tBPAR in treatment group i , n_i is the number of patients in treatment group i and θ_i is the probability of tBPAR.

The efficacy analysis for the first 3 months of Part 2 considers whether a CFZ533 treatment arm meets the pre-defined criteria for initiation of Part 3.

The pre-defined success criteria is considered to be a tBPAR rate difference between the CFZ533 arm and the control group of less than 20 percentage points with at least 60% level of proof.

$$\Pr(\theta_{\text{CFZ533}} - \theta_{\text{SoC}} < 0.20 \mid \text{data}) > 60\%$$

The required posterior probabilities will be estimated from simulations of the posterior distributions of $\theta_{\text{CFZ533}} - \theta_{\text{SoC}}$ and compared to the thresholds for the levels of proof.

The prior distributions will be assumed to be a non-informative Beta(1/3, 1/3) for CFZ533 and an informative prior of Beta(1, 13) for SoC. This informative prior corresponds to an approximate mean response rate of 7% with a 95% confidence interval of (0.2%, 24%) and was determined via a meta-analysis of control therapies.

The posterior mean tBPAR rates for each treatment group and for the difference in mean response rates between treatments will be tabulated together with the 95% credible intervals, the number of patients with tBPAR and the posterior probabilities of being above the thresholds, 10%, 15%, 20%, 25%.

